Life-threatening pancreatitis has occurred both in children and adults. Some cases described as hemorrhagic with rapid progression from initial symptoms to death. Can occur shortly after initial use as well as after several years of use. Warn patients and caregivers that abdominal pain, nausea, vomiting, and/or anorexia can be symptoms of pancreatitis that require prompt medical evaluation.

Usually discontinue the drug and initiate alternative therapy if pancreatitis is diagnosed.

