Patients will be randomized to active treatment or control stratified by lung re-expansion ($\geq 80\%$ lung re-expansion, $<80\%$ lung re-expansion), ECOG performance status (0-1, 2, 3), using the Clinical Trial Conduct website (<https://biostatsitics.mdanderson.org/ClinicalTrialConduct>), which is housed on a secure server at MDACC and maintained by the MDACC Department of Biostatistics. Access to the website will be gained through usernames and passwords provided by the MDACC Department of Biostatistics to personnel responsible for enrolling patients and reviewing and analyzing patient data. Training on the use of the Clinical Trial Conduct website to randomize and enroll patients on the study will be provided by the study statistician. Investigation Pharmacy will have access the Clinical Trial Conduct website

to review the patient assignment. The IND office will be notified if an event occurs leading to the un-blinding of the randomization.

Toxicity Monitoring

We will use the methods described by Thall et al. (1995) to monitor the rate of toxicity leading to dose reduction for patients on active treatment. Because the study is blinded to the investigators, the study statistician will monitor the toxicity monitoring rule for the active treatment arm. Toxicity data leading to dose reduction will be forwarded to the study statistician as they accrue in the form of an email with the patient study identifier and a description of the toxicity leading to dose reduction.

If the rate of toxicity leading to dose reduction for patients on active treatment is more than 25% the study will be stopped. We will enroll a minimum of 10 and a maximum of 40 patients on active treatment. We will stop the study early if $P(\text{toxicity leading to dose reduction for patient on active treatment} > 25\% | \text{data from the study}) > 0.975$. That is, given the toxicity outcomes from the patients on active treatment, if we determine that there is more than a 97.5% chance that the rate of toxicity leading to dose reduction is more than 25% we will stop the study. This decision rule gives the following stopping rule. We assume a uniform prior distribution for the rate of toxicity leading to dose-reduction. Stop the study if

[# of pts on active treatment with toxicity leading to dose reduction / # of pts evaluated]
> 6/10, 8/15, 9/20, 11/25, 13/30, 14/35, 16/40

The operating characteristics of this study design are shown in the table below.

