7.0 Criteria for Removal from the Study

7.0 Criteria for Discontinuation on Study

Patients will be removed from the study for any of the following reasons:

1. Patient requests to withdraw.
2. The patient is unwilling or unable to comply with study requirements.
3. There is an unrelated intercurrent illness that will affect assessment of clinical status to a significant degree as determined by the principal investigator or the treating physician.
4. The treating physician or investigator must discontinue study if he/she thinks that the patient's health or well-being is threatened by continuation on study.
5. Identification of recurrent or new cancer.

If any safety parameters show a clinically significant change from baseline that warrants early termination of treatment, the patient will continue with the scheduled study-related procedures. Appropriate safety monitoring will continue until the patient is discharged from the study. The reason for and date of the discontinuation will be obtained.

Participants have the right to withdraw from study at any time. If a participant chooses to withdraw, he/she should contact the principal investigator and/or research nurse who will provide any necessary instructions for finalizing removal from study. If the patient requests to withdraw his/her samples (i.e. residual pleural fluid, blood), appropriate personnel will be notified and samples will be withdrawn and destroyed as per UTMDACC Institutional Laboratory Guidelines. If a patient is non-compliant or lost to follow-up, the research nurse or his/her designee will make three attempts to call the patient over the period of one month. These attempts will be documented. If the research nurse or his/her designee is unable to make contact with either the patient or a family member after three phone calls, then a letter will be sent to the patient's last known address. If after one month from the letter's sent date there is no response from the patient or family member then the patient will be withdrawn from study.

Precautions for Treatment

VPA should not be administered to pregnant women. A negative pregnancy test should be confirmed before administration of VPA.

Concomitant Treatment

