7.2 Replacement of Subjects

Participants who withdraw from the study prior to completion of the study treatments for reasons other than serious adverse events, unacceptable toxicity or progressive disease will be defined as dropouts and will be replaced. Replacement participants will be assigned the next sequential number.

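### The toxicity stopping rule counts only dose reductions, and the plan does not say that a patient who stops study drug outright for toxicity is an event

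*Combined protocol and SAP*

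**What the plan says.** Section 6.0, Toxicity Monitoring, sets out to "monitor the rate of toxicity leading to dose reduction for patients on active treatment". The study stops if there is "more than a 97.5% chance that the rate of toxicity leading to dose reduction is more than 25" percent. The prior is stated: "We assume a uniform prior distribution for the rate of toxicity leading to dose-reduction". The monitored sample is also stated: "We will enroll a minimum of 10 and a maximum of 40 patients on active treatment". The boundary is "6/10, 8/15, 9/20, 11/25, 13/30, 14/35, 16/40", where the numerator is active-arm patients with dose-reducing toxicity and the denominator is patients evaluated, a term that is not defined.

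Because the investigators are blinded, the study statistician applies the rule. The case information that the section sends to the statistician is an e-mail for each toxicity that led to a dose reduction. The operating-characteristics table, and in the Toxicity subsection the 90% credible interval and the posterior probability of exceeding 25%, use the same event.

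Elsewhere the document foresees stopping the drug:
- Section 7.0: "If any safety parameters show a clinically significant change from baseline that warrants early termination of treatment", the patient stays on the scheduled study procedures.
- Section 7.2 replaces patients who withdraw for "reasons other than serious adverse events, unacceptable toxicity or progressive disease", so it recognises withdrawal for unacceptable toxicity and does not replace those patients.
- The boxed-warning text in 5.1.4 reads: "Usually discontinue the drug and initiate alternative therapy if pancreatitis is diagnosed".

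**The concern.** A rule meant to stop the study for excess toxicity should count the toxicities that end treatment as well as those that lower the dose. As worded, it is built on dose reduction alone. A patient who stops for toxicity without an earlier reduction generates no e-mail. Section 7.0 keeps a patient whose treatment ends early for safety on scheduled procedures, so that patient plausibly remains among those evaluated and is then counted as free of toxicity.

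At stake is the sensitivity of the only numerical toxicity rule in the plan. The observed rate would understate treatment-changing toxicity by exactly the share of patients who go straight to a stop. Two statisticians could also count the same discontinuation differently.

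**Working it through.** **Inputs from Section 6.0.** Uniform prior, Beta(1,1); limit 0.25; posterior cut-off 0.975; looks at 10, 15, 20, 25, 30, 35 and 40 active patients; the printed boundary and the printed table.

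**Step 1: reproduce the boundary.** After r events in n patients the posterior is Beta(1 + r, 1 + n − r). The boundary is the smallest r with P(rate > 0.25) > 0.975. At n = 10, r = 5 gives 0.9657 and r = 6 gives 0.9924, so 6. At n = 40, r = 15 gives 0.9667 and r = 16 gives 0.9848, so 16. All seven printed boundaries are reproduced.

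**Step 2: reproduce the table.** An exact sequential binomial calculation, stopping when the count reaches the boundary at looks 10 to 35 (a stop at 40 is not early), gives:

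| Rate | Plan | Recomputed |
|---|---|---|
| 0.20 | 0.020 | 0.019 |
| 0.25 | 0.071 | 0.075 |
| 0.30 | 0.205 | 0.204 |
| 0.35 | 0.407 | 0.407 |
| 0.40 | 0.636 | 0.635 |
| 0.45 | 0.827 | 0.821 |

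All agree within 0.01. The boundary is printed with a strict inequality, but the table is reproduced only if reaching the boundary is enough: the strict reading gives 0.477 at a rate of 0.40. The arithmetic of the rule is sound, so the question is only what is counted.

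**Step 3: an example that needs no assumed rate.** Suppose that among the first 10 active patients 5 have a dose reduction and 5 stop outright for toxicity. All 10 have had treatment-changing toxicity. The count is 5/10, below 6/10, and the rule does not stop the study. Likewise, at 40 patients, 15 reductions plus any number of outright stops do not reach 16/40.

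**Step 4: effect on the stopping probability.** Let T be the total rate of toxicity leading to reduction or outright stop, and s the share of those patients who stop with no earlier reduction. If they stay in the denominator, the rule sees T × (1 − s). The documents give neither T nor s. Both are assumptions here, with s ranging from 0% to 50%. For T = 0.40:
- s = 0%: 0.40 × 1.00 = 0.40
- s = 25%: 0.40 × 0.75 = 0.30
- s = 50%: 0.40 × 0.50 = 0.20

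The probabilities of stopping early, computed as in Step 2, are:

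| T | s = 0% | s = 25% | s = 50% |
|---|---|---|---|
| 0.30 | 0.204 | 0.039 | 0.003 |
| 0.40 | 0.635 | 0.204 | 0.019 |
| 0.50 | 0.932 | 0.522 | 0.075 |
| 0.60 | 0.996 | 0.821 | 0.204 |

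The first column is also what the rule delivers if outright stops are counted. Prior, limit and cut-off are unchanged, so the boundary is too.

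**The case against.** The strongest reply is that the document is silent and excludes nothing. It never says that a discontinuation is not an event, and it does not define who is evaluated. A reader might infer that the plan deliberately leaves out toxicity that ends treatment. The text does not support that: the gap comes from the wording and the data flow, and one sentence could close it.

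Second, the gap matters only for patients who stop with no earlier reduction; those reduced first are already counted. The example tables in Section 5.2 show stepwise reductions. Section 5.3.1 frames changes in amylase, lipase and liver enzymes as guidance on dose reduction, and the management figures that would show which events lead straight to a stop are not available to this review. The pancreatitis sentence is boxed-warning text, qualified by its first word, and Section 7.2 does not say whether a reduction came before the withdrawal. These passages show that stopping can occur, not how often it occurs without a reduction. This point stands, and it is why the size is given as a range.

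Third, a reader might infer that a harmful drug could go unnoticed. That goes too far. Section 8.1 sends every serious adverse event to the IND Office whatever its attribution, with faster reporting of unexpected related fatal or life-threatening events. Section 5.2 provides for unblinding and notice to the IND monitor when the drug level is abnormally high. Section 5.1.6 promises a toxicity review at half accrual, and adverse events are tabulated at the end. These safeguards still operate. None is a numerical rule that counts discontinuations, and the half-accrual review has no threshold of its own.

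**Conclusion.** The point holds as a gap in the event definition and in the reporting to the statistician. Followed literally, the rule can fail to stop when treatment-changing toxicity is well above the limit, as the 10-patient example shows without any assumed rate. At an assumed total rate of 40%, the probability of stopping early falls from about 0.64 to 0.20 if a quarter of toxic patients stop outright, and to 0.02 if half do. If none do, nothing is lost. These figures assume that outright stops remain among the patients evaluated, are not reported as reductions, and that reaching the boundary is enough to stop. The documents do not support taking any one of them as the expected loss.

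**What to change.** Define the monitored event as toxicity that leads to dose reduction or to permanent discontinuation of study drug, including treatment-related death, and say that patients who discontinue for toxicity are among those evaluated. Forward all such cases to the study statistician. Keep the prior, the 25% limit, the 0.975 cut-off and the boundary; relabel the operating-characteristics table; and use the same event for the credible interval and posterior probability in the Toxicity subsection. If this is already the intention, one sentence stating it is enough.

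Do not add interruptions. Nothing above calls for them, and with concurrent chemotherapy allowed they could change what a 25% limit, set for dose reductions, means.

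The cost is one definition, one e-mail form and a relabelled table. The downside is that the rule will stop more often to the extent that outright discontinuations for toxicity occur.

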6.0 Statistical Considerations

6.0 Statistical Considerations

Sample Size

The primary outcome for this study is time to pleural catheter removal because it is no longer needed to drain the pleura of fluid. Patients who have their catheter removed for other reasons will be censored as of the date of catheter removal. Patients who die before having their catheter removed will be censored on the date of death.

Preliminary data from 58 breast cancer patients with ECOG performance status 0, 1, 2, or 3 revealed a median time to catheter removal of 110 days with 95% confidence interval 56 to 328 days. Twenty-nine of these 58 patients had their catheters removed because they were no longer needed to drain the pleura of fluid.

Patients will be randomized to active treatment (valproic acid) or control. A sample size of 76 patients (38 on each arm) will yield 80% power to detect an improvement in median time to catheter removal from 56 days in the control arm to 28 days (hazard ratio = 2.0) in the active treatment arm with a 2-sided significance level of 0.05. We expect to enroll 3 patients per month. We will be able to detect a hazard ratio of 2.0 (control vs. experimental), regardless of the median for the control group. If the median for the control group is actually 110 days, then we will be able to detect a significant difference if the median in the experimental group is 55 days.

This sample size calculation includes an interim analysis for futility and for efficacy once 36 patients have had their catheters removed using the methods of Lan and DeMets. The interim analysis for efficacy will employ an O'Brien-Fleming stopping boundary with a nominal significance level of 0.0031, while the interim analysis for futility will employ a Pockock stopping boundary with a nominal significance level of 0.3217. The final analysis will use a nominal significance level of 0.049 and will be conducted after all patients have had their catheters removed. These sample size calculations were performed with East 5.0 (Copyright © 2007, Cytel Inc., Cambridge, MA). Sample size was calculated based on 50% reduction in median time to catheter removal secondary to improved fluid in the control.

Randomization

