Operating Characteristics of Toxicity Monitoring Rule					
Rate of Toxicity Leading to Dose Reduction	Probability of Stopping Early	Sample Size			
		P_{25}	P_{50}	P_{75}	
0.20	0.020	40	40	40	
0.25	0.071	40	40	40	
0.30	0.205	40	40	40	
0.35	0.407	20	40	40	
0.40	0.636	15	30	40	
0.45	0.827	10	20	35	

Analysis

We will use summary statistics to describe the demographic and clinical characteristics of patients on each treatment arm.

Primary Outcome

Time to catheter removal will be measured from the date of placement of the catheter to the date it is removed. Removal of the catheter because it is no longer needed to drain the pleura will be considered an event. Removal of the catheter for other reasons will be considered competing risks. Patients who die before their catheter is removed will be considered censored on the date of death. We will use the methods described by Gooley et al. (1999) to estimate the cumulative distribution of time to catheter removal stratified by treatment arm and randomization strata.

We will use Cox (1972) proportional hazards regression to model time to catheter removal as a function of treatment arm, cytology, and lung re-expansion, as well as other potential prognostic factors, including ECOG performance status, the number of circulating tumor cells in the peripheral blood and in the pleural effusion.

Secondary Outcomes

We will use summary statistics to describe the amount of pleural fluid drainage by treatment arm, and we will use a two-sample t-test to compare treatment arms with respect to the mean amount of pleural fluid drainage. If the usual normality assumptions do not hold we will use the Mann-Whitney test to compare treatment arms with respect to the median amount of pleural fluid drainage.

We will compare treatment arms with respect to tumor burden using a Cochran-Mantel-Haenszel chi-square test stratified by concomitant therapy. Tumor burden will be assessed with chest cat scan during week 10.

We will use summary statistics to describe symptom burden dyspnea and exercise tolerance changes and dyspnea as measured by the EQ-5D and St George's respiratory questionnaire at baseline and again at weeks 2, 6, and 10. We will use repeated measures analysis of variance methods to assess differences between treatment arms with respect to QOL, dyspnea and exercise tolerance

Toxicity

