We will estimate the rate of toxicity leading to dose reduction for patients on the active treatment with a 90% credible interval. If we have toxicity leading to dose reduction in 5 of the 40 patients on the active treatment, then our 90% credible interval for the rate of toxicity leading to dose reduction will be 6.6% to 23.6%. We will also report the posterior probability that the rate of toxicity leading to dose reduction for patients on the

active treatment is more than 25%.

We will tabulate adverse events by treatment arm, grade, and relationship to study drug.

Translational Studies

For CTC studies using the adnagen approach .3 ng/ml in GA733-2 or muc-1 will be considered positive and both conversion to negative and change from baseline (using continuous data) will be assessed. Descriptive statistics will be applied. Using the Veridex system 5 CTCs will be considered positive for all dichotomous analyses and conversion to negative and change from baseline will be assessed as above.

Statistically significant conversion to negative in the VPA arm in either test will be considered a significant change. CTC studies will be performed only if funds are available and will be done by [name] who has extensive experience with both tests.

For quiescence and stem cell analysis flow cytometry will be performed for cell cycle, CD44+CD24-CD45-Epcam+ and aldefluor. Samples will be divided into three replicates to address run variability. Total percent quiescent (G1/G0) epithelial cells will be the primary metric for correlative evaluation although quiescence within stem cell populations will be assessed and reported. All data are continuous variables.

Dichotomous analysis will be based on values > or <= to the median for the entire dataset for each variable. All biomarker analyses related to outcome will be performed according to REMARK guidelines incorporating time to metastases, extent of metastatic disease (multiple vs. effusion only), triple negative vs. not, extent of prior therapy, and KPS. Analysis will include correlation between percent quiescent cells and time to catheter removal in both arms and change in percent quiescent cells from baseline in both arms. Given there will be significant variation in the baseline G0/G1 measurement we will consider a 30% relative increase in G0/G1 from baseline significant.

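### The toxicity stopping list in section 6.0 carries a strict > sign, but the stated posterior rule and the operating characteristics table both require ≥

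*Combined protocol and SAP*

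**What the plan says.** The Toxicity Monitoring part of section 6.0 states the criterion as a formula and again in words. The study stops "if we determine that there is more than a 97.5% chance that the rate of toxicity leading to dose reduction is more than 25" per cent. The prior is given: "We assume a uniform prior distribution for the rate of toxicity leading to dose-reduction". So is the range of monitoring: "We will enroll a minimum of 10 and a maximum of 40 patients on active treatment". The section then says "This decision rule gives the following stopping rule", and the ratio of patients with a dose-reducing toxicity to patients evaluated is compared with "> 6/10, 8/15, 9/20, 11/25, 13/30, 14/35, 16/40".

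A table headed "Operating Characteristics of Toxicity Monitoring Rule" follows. It gives the probability of stopping early and the quartiles of the active-arm sample size for true rates from 0.20 to 0.45.

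**The concern.** The list is offered as a consequence of the posterior rule, so the two should give the same decision at every count. They do not at exactly 6 of 10, 8 of 15, 9 of 20 and so on: the posterior rule says stop, and the list with > says continue.

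This is a safety rule that can end the trial, and a list of counts is the natural thing to check against when toxicities reach the study statistician one at a time by email. The counts in dispute are also the usual way of crossing. Among trials that the posterior rule stops before the 40th patient, most first cross exactly on a listed count (shares in the working). Anyone using the list as printed would not obtain the stopping probabilities that the protocol states.

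**Working it through.** **Inputs, all from section 6.0.** Prior Beta(1,1); reference rate 0.25; cut-off 0.975; looks at 10, 15, 20, 25, 30, 35 and 40 active-arm patients; the listed counts; the table of operating characteristics.

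**Step 1: are the listed counts the smallest that trigger the rule?** With x toxicities in n patients the posterior is Beta(1 + x, 1 + n − x), and the rule needs P(rate > 0.25) > 0.975.

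| n | listed x | posterior at x − 1 | posterior at x |
|---|---|---|---|
| 10 | 6 | 0.9657 | 0.9924 |
| 15 | 8 | 0.9729 | 0.9925 |
| 20 | 9 | 0.9439 | 0.9794 |
| 25 | 11 | 0.9599 | 0.9845 |
| 30 | 13 | 0.9711 | 0.9885 |
| 35 | 14 | 0.9539 | 0.9791 |
| 40 | 16 | 0.9667 | 0.9848 |

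Every listed count is above 0.975 and every count one lower is below it. The list is therefore the exact boundary for stopping at or above these counts. Cut-offs of 0.95, 0.98, 0.985 and 0.99 were also tried with the uniform prior, and none returns this list.

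**Step 2: which sign reproduces the table?** An exact binomial recursion was run over the looks from 10 to 35, removing at each look the paths that stop. Early means before the 40th patient.

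| true rate | table | with ≥ | with > | quartiles, table | quartiles, ≥ | quartiles, > |
|---|---|---|---|---|---|---|
| 0.20 | 0.020 | 0.0186 | 0.0049 | 40/40/40 | 40/40/40 | 40/40/40 |
| 0.25 | 0.071 | 0.0746 | 0.0284 | 40/40/40 | 40/40/40 | 40/40/40 |
| 0.30 | 0.205 | 0.2035 | 0.1031 | 40/40/40 | 40/40/40 | 40/40/40 |
| 0.35 | 0.407 | 0.4069 | 0.2573 | 20/40/40 | 20/40/40 | 35/40/40 |
| 0.40 | 0.636 | 0.6348 | 0.4770 | 15/30/40 | 15/30/40 | 20/40/40 |
| 0.45 | 0.827 | 0.8206 | 0.7005 | 10/20/35 | 10/20/35 | 20/25/40 |

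With ≥ the largest gap is 0.827 − 0.8206 = 0.0064. With > the gaps at 0.30 to 0.45 are 0.102, 0.150, 0.159 and 0.127.

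One cell can be checked by hand. At rate 0.45 the table's lower quartile is 10, so at least 25% of trials must stop at the first look. P(X ≥ 6 of 10) = 0.262 satisfies this; P(X ≥ 7 of 10) = 0.102 does not.

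**Step 3: sensitivity.** If stopping at the 40th patient is also counted as early, > gives 0.114, 0.285, 0.522 and 0.748 at rates 0.30 to 0.45, still well below the table. Monitoring after every patient does not reproduce the table either (0.489 at 0.35 and 0.711 at 0.40).

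**Step 4: how often the sign decides.** Probability that the first crossing falls exactly on a listed count, divided by the probability of stopping early under ≥:
- 0.30: 0.159 / 0.204 = 78%
- 0.35: 0.299 / 0.407 = 73–74%
- 0.40: 0.435 / 0.635 = 69%
- 0.45: 0.518 / 0.821 = 63%

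**Step 5: patients treated.** Mean active-arm number, ≥ against >, with trials that do not stop completing at the planned 38 per arm ("A sample size of 76 patients (38 on each arm) will yield 80% power"):
- 0.30: 34.53 against 36.56, difference 2.03
- 0.35: 31.06 against 34.41, difference 3.35
- 0.40: 26.66 against 31.02, difference 4.36
- 0.45: 22.15 against 26.83, difference 4.68

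Completing at the stated maximum of 40 gives slightly larger differences, for example 27.39 against 32.06 at rate 0.40.

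**The case against.** The arithmetic is not in dispute. The case on the other side is that this may not be an error in the plan, and that it would be unlikely to do harm.

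- **The sign may be an artefact of reading the PDF.** Comparison signs are unreliable in this text. The adverse-effect list appears in both section 1.2.2 and section 5.1.4, and the back pain and increased appetite entries have a dot before the percentage in one and > in the other. Against that, a ≥ survives in the Randomization paragraph of section 6.0 and a ≤ in section 7.1. The text available cannot settle it, and this point stands as a limit on the finding.
- **The governing rule is stated correctly.** The formula, the sentence in words, the prior and the table all agree, and the list is only derived from them. That is true, and it means anyone who computes the posterior is unaffected.
- **The operator is a statistician.** Section 6.0 gives the monitoring to the study statistician, and its Toxicity paragraph adds "We will also report the posterior probability that the rate of toxicity leading to dose reduction for patients on the" active treatment is above 25%. This lowers the chance of misuse. It does not remove the contradiction, because the list is the form of the rule that is easiest to apply.
- **The excess numbers are idealised.** They assume that each group is fully evaluated before more patients enter. Continued enrolment during evaluation would shrink them somewhat. At true rates of 0.20 and 0.25 the two signs differ by only about 0.3 and 0.9 patients (completing at 38).

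**Conclusion.** The concern holds. As the text reads, the sign before the list contradicts both the posterior rule it is said to follow from and the table computed from that rule. The counts, prior, cut-off and table are consistent with one another; only the sign is out of line.

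Followed literally, the list would halve the chance of early stopping at a true rate of 0.30 (0.204 to 0.103). It would lower it by 15 to 16 percentage points at 0.35 and 0.40, and by 12 points at 0.45. The cost is about 2.0 to 4.7 more patients treated on an active arm of 38.

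These sizes assume that the list is used in place of the posterior criterion, that looks fall at every fifth patient from 10 with complete evaluation, and that no other stopping rule intervenes. Whether the sign is the author's or was lost in reading is open, so confidence that the plan itself is wrong is medium. If the source prints ≥, the point falls away. If it prints >, it should be fixed, because it concerns a threshold for stopping the trial.

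**What to change.** Look at the source document for a ≥ in front of the list in section 6.0. If it prints >, reconcile the list with the stated posterior rule and the operating characteristics table by printing ≥ there. Leave the counts, prior, 0.975 cut-off, table and sample size as they are. The cost is one symbol, with no recalculation.
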